#### 4. Study endpoint criteria

- A. Patient Completion of Study: If a study patient has completed the final visit (Visit 5) of the study, he/she is considered to have completed the study.
- B. Patient Discontinuation: Each study patient may voluntarily discontinue the study at any time they choose. Study patients who cannot complete the study for administrative reasons (e.g., non-compliance, failure to meet visit schedule, etc.) will be discontinued from the study. Study patients discontinued during the enrollment phase (prior to surgery) of the study will be replaced.
- C. Patient Termination: A study patient will be terminated if the study patient develops any severe adverse event that may be related to the study. A study patient will receive appropriate treatment at the discretion of the investigator. Notification of termination will be clearly documented. These study patients are considered to have completed the study and will not be replaced.

- D. Study Termination: The investigator with appropriate notification may terminate the study. If, after clinical observations, the investigator feels that it may be unwise to continue the study, he may stop the study.
- E. Study Completion: The study will be complete when all enrolled patients have completed Visit 5 or have been terminated from the study.

## 5. STATISTICAL CONSIDERATIONS

### A. Sample size

A total of 40 subjects will be enrolled. In order to calculate the sample size, we need to know an accurate estimate of the standard deviation of the outcome measure which we do not know; therefore, we consider this study a pilot trial. When estimating the sample size for a pilot study, the simplest method is to apply a sample size rule of thumb.

Browne suggests a general flat rule to 'use at least 30 subjects or greater to estimate a parameter'. However, since analysis comparing manual phaco vs. femtosecond laser assisted cataract surgery will be conducted, at least 20 subjects will be enrolled in each surgical technique (femtosecond laser/manual phaco)

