#### B. Surgery Procedures:

The first eye undergoing surgery will be randomized to either the Quatera® 700 or the Centurion® Vision System. The fellow eye will receive the alternate treatment. The first operative eye will be the eye with the worse cataract. If the cataract is the same in both eyes, the clinic's standard of care will be followed. The randomization list will be provided by a third-party consultant. Research staff not attending or participating in surgery will be masked to the extent possible.

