### D. Measurements and evaluations

1. Visit 0: Informed consent process will be conducted at this visit. Assessments include best-corrected distance visual acuity (BCDVA, Snellen chart), manifest refraction, intraocular pressure (IOP, Goldman), corneal tomography (Pentacam), ultrasound pachymetry, specular microscopy, macular OCT, slit lamp examination including dilated fundus exam, cataract density and type (LOCS III). Any testing that is part of the site's standard of care preoperative cataract surgery evaluation may be performed prior to the informed consent being signed provided these tests are conducted within 90 days of the surgery and notation of the date performed is entered onto the CRF. The surgeon's standard pre cataract surgery treatment will be used in all his patients

First eye undergoing surgery will be randomized to Group A (Quatera 700) or B (Centurion).

2. Visit 1: The surgeon may use his preferred small incision cataract extraction technique (manual phacoemulsification or laser assisted). The same technique must be used in both eyes. The intraocular lens will be implanted in the bag. The following information will be captured the day of surgery: phaco metrics, lens removal time, duration of surgery, incision size (prior to lens implantation), estimated fluid used, lens implanted and power, target refraction for IOL power implanted, additional surgical procedures, intraoperative complications, and any device deficiencies. Additionally, the surgery will be recorded, and the videos will be analyzed digitally using the Surgery Optimizer and manually using a stopwatch. The surgeon's standard post cataract surgery treatment will be used in all patients.

3. Visit 2: monocular pinhole uncorrected visual acuity (UCVA), slit lamp examination, IOP, ultrasound pachymetry and Pentacam.
4. Visit 3: Manifest refraction, best distance corrected visual acuity (BCVA), IOP, slit lamp examination, ultrasound pachymetry, Pentacam and macular OCT.
5. Visit 4: Manifest refraction, best distance corrected visual acuity (BCVA), IOP, slit lamp examination, ultrasound pachymetry, Pentacam, macular OCT, and dilated fundus exam if deemed necessary by the investigator.
6. Visit 5: Manifest refraction, best distance corrected visual acuity (BCVA), IOP, slit lamp examination, ultrasound pachymetry, Pentacam macular OCT will be performed. Dilated fundus exam to be performed if deemed necessary by the investigator.

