### C. Study Endpoints:

#### 1. Primary Endpoints:

- a. Central corneal thickness at day 1 postoperatively
- b. Lens removal time (from end of rhexis to complete nucleus removal)

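### The enrolment of 40 is set by a femtosecond-versus-manual comparison that is not randomised, has 20 subjects per group, and carries no stated limit on its interpretation

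*Combined protocol and SAP*

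**What the plan says.** **Sample size (5.A).** The plan states "A total of 40 subjects will be enrolled". It gives no power calculation, because that would need "an accurate estimate of the standard deviation of the outcome measure which we do not know", and it calls the trial a pilot. It cites a rule of thumb to "use at least 30 subjects or greater to estimate a parameter". It then departs from that rule and sets a minimum for each technique: "at least 20 subjects will be enrolled in each surgical technique (femtosecond laser/manual phaco"). The reason given is a planned comparison of the two techniques.

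**What is randomised (3.B and 8.B).** The device for the first eye is randomised, and the fellow eye gets the other device. The first eye is the one with the worse cataract. "The randomization list will be provided by a third-party consultant", and 8.C adds sequentially numbered envelopes. None of these sections mentions stratification or blocking.

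**How technique is chosen (3.D, Visit 1).** "The surgeon may use his preferred small incision cataract extraction technique (manual phacoemulsification or laser assisted"), with the same technique required in both eyes. The exclusion criteria also rule out a different technique in each eye.

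**Analysis (1, 5.B, 5.C).** The objective names only the device comparison. No primary, secondary or exploratory endpoint is tied to technique. Section 5.B provides descriptive statistics and whatever tests suit the data, all two-sided at 5%, and says that groups will be compared.

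**The concern.** The comparison that fixes the sample size is the one that the design protects least. Device is compared within a patient and by randomisation. Technique is compared between patients, by surgeon's choice, on an outcome that the plan does not name. If the plan is followed as written, a difference between laser and manual patients could be reported as significant at 5% and read as an effect of technique, when it may only reflect which patients were selected for laser.

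Two further matters follow. The only quantitative justification offered, the 30-subject rule, does not reach the groups of 20 that produced the total. And if technique is to be used as a subgroup for the device question, device order should be balanced within each technique. Order is tied to cataract severity, since the worse eye is operated on first, and nothing in the plan secures that balance.

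**Working it through.** **Inputs from the documents.** 40 subjects, hence 40 within-subject device pairs; at least 20 subjects per technique; a rule of at least 30 per parameter (all 5.A); two-sided 5% level (5.B). No SD, effect size, power or dropout rate is given, so results are in SD units and 80% power is an assumption.

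**1. The plan's own figure.** 2 × 20 = 40, which reproduces the total. The cited rule alone gives 30, and the rule applied within each technique gives 2 × 30 = 60. Neither equals 40, so the total comes from the technique minimum.

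**2. Precision of the device comparison.** The 95% half-width of a mean paired difference is t(0.975, n−1)/√n, in units of the SD of the paired difference.
- 40 pairs: 2.023/√40 = 0.320
- 20 pairs, within one technique: 2.093/√20 = 0.468

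The detectable paired difference at the assumed 80% power (noncentral t) is 0.45 SD with 40 pairs and 0.66 SD with 20.

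**3. Precision of the technique comparison.** For 20 versus 20 the half-width is t(0.975, 38) × √(2/20) = 2.024 × 0.316 = 0.640, in units of the between-subject SD of the outcome. The detectable difference at the assumed 80% power is 0.91 SD. The SDs in steps 2 and 3 are different quantities, so the half-widths should not be compared as if they shared a scale.

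**4. What the rule of 30 buys.** The 95% limits for an SD, as multiples of its estimate, are √[(n−1)/χ²(0.975)] and √[(n−1)/χ²(0.025)], each on n−1 degrees of freedom.

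| n | lower | upper |
|---|---|---|
| 20 | √(19/32.85) = 0.76 | √(19/8.907) = 1.46 |
| 30 | √(29/45.72) = 0.80 | √(29/16.05) = 1.34 |
| 40 | √(39/58.12) = 0.82 | √(39/23.65) = 1.28 |

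The 40 pairs exceed the cited rule. A technique group of 20 falls short of it.

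**5. Device-order balance within a technique of 20.** The chance of a 14:6 or more uneven split depends on how the list is built, which the plan does not say.
- Simple randomisation: 2 × P(X ≥ 14), X ~ Binomial(20, 0.5) = 2 × 0.0577 = 11.5%
- List balanced 20:20 over the 40 subjects, with 20 per technique: P(X ≥ 14) + P(X ≤ 6), X hypergeometric (40, 20, 20) = 2.6%

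These are probabilities of imbalance. No resulting bias in any estimate has been calculated.

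**The case against.** The trial's stated purpose is the device comparison, and it is sound on this point: it is randomised and paired, and its 40 pairs satisfy a rule worded per parameter, not per group. Section 5.A introduces 20 per technique as a separate minimum and does not claim that the rule of 30 justifies it. Section 5.B permits purely descriptive reporting and does not commit the analyst to a significance test of technique. The trial also calls itself a pilot. All of this stands, and it limits the concern to the technique comparison and to estimates within a technique. It does not remove it: 5.A says that the comparison will be done and sets the enrolment by it, nothing says that it is observational, and any test that is run would be read at 5%.

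Three stronger readings are tempting and are not supported.
- A reader might infer that the lens-removal clock starts at a different event in laser eyes. The documents give one definition for every eye, "Lens removal time (from end of rhexis to complete nucleus removal"), and do not describe how or when the capsule is opened by laser. At most, the plan does not say how the end of rhexis is timed in laser eyes. Since both eyes share a technique, an offset common to laser eyes would largely cancel in the device difference and would mainly affect the technique comparison.
- A reader might infer that the list is unstratified. The plan is silent, so the most that can be said is that stratification is not stated.
- A reader might infer that nobody lost after surgery begins is replaced. Section 4 replaces discontinuations before surgery and excludes replacement after adverse-event terminations, but does not address other later losses.

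**Conclusion.** The concern holds for the technique comparison. It sets the total of 40, yet it is between patients, confounded by surgeon's choice, without a named outcome or analysis, and open to testing at 5% with no caveat. Its half-width is 0.64 SD and its detectable difference 0.91 SD. More subjects would narrow the interval but would not remove the confounding.

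The randomised device comparison is not undermined. Its half-width is 0.32 SD of the paired difference with 40 pairs, widening to 0.47 SD within a technique of 20. The cited rule supports the first of these and not the second.

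These figures assume exactly 20 evaluable subjects per technique, no losses and approximately normal data. The detectable differences also assume 80% power, which the plan does not state. The order-imbalance risk lies between 2.6% and 11.5% for the two list constructions considered. The evidence does not justify redefining the start of a primary endpoint.

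**What to change.** 1. In 3.B and 8.C, require the planned technique to be recorded before the envelope is opened, and stratify the randomisation list by technique with balanced allocation in each stratum, so that device order is balanced within each technique.
2. In 5.A and 5.B, state that femtosecond versus manual is a non-randomised, descriptive comparison, name the outcomes it covers, and report it as estimates with 95% confidence intervals and no claim of significance.
3. In 5.A, add the precision obtained: ±0.32 SD of the paired difference with 40 pairs, ±0.47 SD within a technique of 20, and ±0.64 SD of the outcome for 20 versus 20 (detectable difference 0.91 SD at an assumed 80% power). Say that the 30-subject rule refers to the device comparison.

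The cost is a revised list and a few sentences of protocol text, with no additional patients or procedures. The small downside is that the technique contrast can no longer be presented as a test.

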### B. Statistical Analysis

All data will be collected by the site and entered into a database. Subjects will be assigned an ID number. Data analysis will be performed without patient identification. Statistical analysis will be performed using standard descriptive statistics and other tests as deemed appropriate based on the characteristics of the data to be analyzed. All statistical tests will be two-sided and interpreted at a 5% significance level. Comparisons between the groups will be made. Data analysis will be conducted by a third-party consultant.

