Although phacoemulsification has fewer complications when compared to previous types of cataract surgeries, it still burdens undesirable side effects, in the form of intraoperative and/or post-operative complications. Anterior segment changes occur after phacoemulsification surgery, and corneal endothelium seems to be the most adversely affected structure with significant loss of corneal endothelial cells density and corneal thickness during cataract surgery. Corneal endothelial cell loss can be caused by the heat originated from the ultrasound, excessive irrigation, turbulence of fluid, bubble generation in the anterior chamber, and direct trauma, leading to a reduced corneal metabolism postoperatively. In severe cases, corneal decompensation may occur, following an ineffective endothelial pumping, resulting in persistent corneal edema, and decreased vision leading to subsequent corneal transplantation. Some factors act as adjuvants to increase the risk of cell damage like intraoperative phacoemulsification time, shorter eyes, and a shallow anterior segment, and because of all that it is important to perform surgery as effectively and safely as possible to avoid disrupting the delicate balance of the eye.

Corneal thickness changes after phacoemulsification can be used to assess surgically induced corneal edema and it was already observed that the degree of permanent corneal endothelial damage is related to the degree of early postoperative corneal swelling. Moderate damage of the corneal endothelium during surgery may lead to a transient increase in corneal thickness, although data about it are contradictory since some authors reported that all patients recovered preoperative values after 4 weeks, while others reported sustained increases up to 6 months or even 1 year postoperatively; however, those discrepancies may reflect inadequate measurement of central corneal thickness (ultrasonic pachymetry) and in the estimation of endothelial cell numerical density. Nowadays modern technology, such as optical low coherence reflectometry, allows more precise measurements of the central corneal thickness and published data show that a moderate decrease in the endothelial cell numerical density does not influence the central corneal thickness, if accurately determined, at various time intervals up to 1 year after surgery.

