## 1. OBJECTIVE:

The purpose of this study is to evaluate the Zeiss Quatera® 700 and compare it to the Centurion® Vision System using the optimized settings for each device in patients undergoing uneventful routine cataract surgery. Main end points include central corneal thickness at day 1 postoperatively and lens removal time (from end of rhexis to complete nucleus removal) as measured digitally by the Zeiss Surgery Optimizer and manually with a stopwatch.

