### **3. Exploratory Endpoint:**

- a. Accuracy of the Surgical Optimizer

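### Two primary endpoints are tested at 5% each with no multiplicity control, success rule or named measurement, so the chance of a false primary win is about 10%, plausibly 11–15% if both measurements of each are tested

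*Combined protocol and SAP*

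**What the plan says.** - **Primary endpoints (Section 5.C.1).** Two are listed. The first is "Central corneal thickness at day 1 postoperatively", with no instrument named. The second is lens removal time, with start and stop points but no measurement method.
- **Significance level (Section 5.B).** "All statistical tests will be two-sided and interpreted at a 5% significance level". The tests themselves are left open: descriptive statistics plus "other tests as deemed appropriate based on the characteristics of the data to be analyzed". The section contains no adjustment, order of testing or statement of whether one or both primaries must succeed.
- **Lens removal time (Section 1, Objective).** It is to be taken "as measured digitally by the Zeiss Surgery Optimizer and manually with a stopwatch". Section 3.D (Visit 1) again lists both methods for the surgical videos. Neither is called primary.
- **Day-1 CCT (Section 3.D, Visit 2, and Table 1).** The day-1 assessments are "monocular pinhole uncorrected visual acuity (UCVA), slit lamp examination, IOP, ultrasound pachymetry and Pentacam". Two of these can give a corneal thickness, and neither is tied to the endpoint.
- **Exploratory endpoint (Section 5.C.3).** "Accuracy of the Surgical Optimizer".
- **Status (Section 5.A).** 40 subjects, described as a pilot, with the standard deviation unknown and the number taken from a rule of thumb.

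**The concern.** The plan never says how the two primary endpoints combine into a conclusion. With each tested at 5%, a report could present either one as the primary finding, and the overall false-positive rate would then exceed the 5% that a reader would assume.

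The open choice of measurement adds to this. For lens removal time, the analyst will hold two values per eye and no instruction on which one is primary. The visit schedule leaves CCT in the same position. The choice could therefore be made after the results are known, and that weakness does not depend on any assumption about correlation. For lens removal time there is a further awkwardness: one of the two methods is itself being assessed for accuracy in the same study.

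**Working it through.** **Inputs from the documents.** Two primary endpoints (Section 5.C.1); 5% two-sided for every test (Section 5.B); two methods for lens removal time (Section 1); two corneal instruments at day 1 (Section 3.D, Table 1); 40 subjects with one eye per device (Sections 2 and 5.A).

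**Assumptions, not in the documents.** A win on any one result counts as a primary win. The correlation between the two measurements of one endpoint is *w*, and the correlation between the two endpoints is *b*. Both refer to the test statistics when there is no true difference.

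**Step 1: the plan's own figures.** One test at 5% has an error rate of 5%. The sample size is 20 per surgical technique × 2 = 40. No overall error rate or power is stated, so there is nothing further to reproduce.

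**Step 2: one measurement per endpoint, two tests.**
- Independent: 1 − 0.95² = 9.75%.
- Correlated endpoints (simulation, 1,000,000 draws): 9.5% at *b* = 0.3, 9.1% at *b* = 0.5, 7.8% at *b* = 0.8. So 10% is a central figure, not a floor.

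**Step 3: both measurements tested, four tests.**
- All independent: 1 − 0.95⁴ = 18.55%. The bound under any dependence is 4 × 5% = 20%.
- With correlated measurements (simulation):

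| *w* | *b* = 0 | *b* = 0.5 |
|---|---|---|
| 0.80 | 15.1% | 13.8% |
| 0.90 | 13.6% | 12.6% |
| 0.95 | 12.6% | 11.5% |
| 0.99 | 11.0% | 10.2% |

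Simulated paired t-tests with n = 40 and *b* = 0 agree: 15.0%, 13.6% and 12.5% at *w* = 0.80, 0.90 and 0.95.

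**Step 4: what each repair achieves.**
- Name one measurement per endpoint but keep 5% for each: still 9.75% if independent.
- Name one measurement and apply Holm (smaller p-value against 2.5%, then the other against 5%): with no true difference on either, 1 − 0.975² = 4.94% if independent, and at most 5% under any dependence.
- Name one measurement and require both endpoints to be significant at 5%: 0.05² = 0.25% if independent with no true difference on either, and never above 5%.

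**Step 5: cost in sensitivity.** For a paired t-test with n = 40 and 80% power, the detectable difference at two-sided 5% is 0.454 SD of the paired differences. At 2.5% it is about 0.454 × (2.241 + 0.842)/(1.960 + 0.842) = 0.50 SD.

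**The case against.** The strongest reply is that the plan does not commit to what the larger figures assume.

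- **A reader might infer that four primary tests will be run and that the error rate is 19%.** The documents do not say so. They list two endpoints. The dual measurement is explicit for lens removal time only; for CCT it is inferred from two devices being scheduled. Section 3.D describes Pentacam as tomography and lists pachymetry separately, so pachymetry may well be the intended source. The 19% also needs two readings of one cornea, and two timings of one video, to be independent, which is not plausible. This objection stands.
- **The plan has no success rule, so inflation is conditional.** If both endpoints had to be significant, with one measurement each, there would be no inflation. This is correct, but the missing rule is itself the gap.
- **A reader might infer that a primary endpoint rests on a tool of unproven accuracy, made under the brand of one compared device.** That goes too far. A stopwatch measurement is also required, Table 1 lists lens removal time and the optimizer on separate rows, and testing the tool's accuracy suggests that the stopwatch is the reference. The brand alone shows no bias. What remains is that the reference role is not stated.
- **A reader might infer that the Introduction supports Pentacam for CCT.** It questions ultrasonic pachymetry but credits optical low coherence reflectometry, and it does not mention Pentacam. It settles nothing between the two scheduled devices.
- **It is a pilot.** This lowers the stakes, but the plan still names primary endpoints and tests them at 5%, and Section 12 intends publication.

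**Conclusion.** The concern holds in a limited form. Two primary endpoints are tested at 5% each without multiplicity control or a success rule. The measurement is undecided explicitly for lens removal time and by omission for CCT.

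If any single win counts, the chance of at least one false primary win is:
- about 10% with one measurement per endpoint (9.1% at an assumed between-endpoint correlation of 0.5);
- plausibly 11–15% if both measurements are tested (assumed within-endpoint correlation 0.8 to 0.99, endpoints uncorrelated; somewhat lower if the endpoints are correlated);
- about 19% only in the limiting case of four independent tests.

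The documents give no correlations, so the last two figures are illustrations. The first needs only the any-win reading and near-independent endpoints. Severity is should-fix: the pilot status reduces the consequence without removing the gap.

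**What to change.** Amend Sections 5.B and 5.C before data are seen. The first two changes settle the measurement and the third controls the error rate; both parts are needed.

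1. **Lens removal time.** Make the stopwatch reading of the surgical video the primary measure. Use the Surgery Optimizer only for the exploratory accuracy analysis, with the stopwatch as the stated reference.
2. **Day-1 CCT.** Name one of the two scheduled instruments as the source of the primary endpoint and call the other supportive. The essential step is to choose in advance; the documents do not decide which.
3. **Two primaries.** Apply Holm at an overall two-sided 5%, or state that both must be significant at 5% for the study to be called positive.
4. **Secondary endpoints.** Report estimates with 95% confidence intervals and label their p-values descriptive. Several are measured at more than one visit, so the number of tests depends on how they are counted; a descriptive label avoids the issue.

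**Cost.** Wording only, with no extra subjects or visits. Under Holm, the first step at 2.5% raises the detectable paired difference from about 0.45 to about 0.50 SD (80% power, n = 40). Under the both-required rule each test stays at 5%, but joint power falls: two independent tests with 80% power each give 0.8 × 0.8 = 64%.
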